8.2.3.2. Planned Adverse Event Safety Statistical Analyses*AESIs Analyses*

Adverse events of special interest are described in Section [10.6.4](#).

Summaries of AESIs will include the number, percentage and rate per 100 person-years of subjects having at least one occurrence, the number of events, the number of subjects by number of occurrence, the characteristics of the AE (serious, drug-related, etc.), outcome, maximum intensity, time to first onset/worsening, and action taken summarized by treatment group. For each count, a subject will be summarized as follows:

- Serious/drug-related/severe/fatal: If any specific AE falls in the respective category, the subject will be counted in that category.
- Outcome: The subject will be counted within a category if there is at least one specific AE in that category.
- Maximum intensity: The specific AE with the maximum intensity will be counted for this purpose. For example, a subject will be counted in the 'severe' category if there is at least one specific AE with severe intensity. A subject will be counted in the 'moderate' category if there is at least one specific AE with moderate intensity and there is no specific AE with severe intensity.
- Time to first onset/worsening (days): The earliest of onset dates for the specific AE – treatment start + 1

CONFIDENTIAL

201410

If the AE onset date/AE worsening and/or resolution date is missing or incomplete in the database for any occurrence of the specific AE, time to first onset /worsening will be left missing for the subject. These summaries of special interest AEs will be provided for those AEs classified as treatment emergent.

Cumulative incidence function (CIF) plots may be produced for each AESI summarizing the time to first occurrence of the AESI by treatment group, with the exception of the composite endpoint AESI (death, myocardial infarction, stroke, heart failure, thromboembolic events, thrombosis of vascular access). This endpoint will use a Kaplan-Meier plot. If there are less than 20 subjects total for both the daprodustat and darbepoetin alfa arm, then these plots will not be created. Competing risks for the AESI cumulative incidence plots include:

AE of Special Interest (Event of interest)	Competing Risk Events
Thrombosis and/or tissue ischemia secondary to excessive erythropoiesis	Death due to any cause prior to the AESI
Cardiomyopathy	Death due to any cause prior to the AESI

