Follow-up	
If AE onset date or AE worsening date is after the last non-zero dose date plus 1 day. AE Start Date $>$ Last Non-Zero Dose Date + 1 day AE Worsening Date $>$ Last Non-Zero Dose Date + 1 day AE worsening during follow-up will be defined relative to the maximum intensity of AE prior to randomized treatment start date.
 
AE worsening date is the first date in the follow-up period, when AE intensity increased relative to the maximum intensity of the AE prior to randomized treatment start date.

Onset /Worsening Time Since 1 st Dose (Days)	
If Treatment Start Date $>$ AE Onset Date: AE Onset Date - Treatment Start Date If Treatment Start Date \leq AE Onset Date: AE Onset Date - Treatment Start Date + 1 If Treatment Start Date $>$ AE Worsening Date: AE Worsening Date - Treatment Start Date If Treatment Start Date \leq AE Worsening Date: AE Worsening Date - Treatment Start Date + 1 Missing otherwise.

Onset /Worsening Time Since Last Dose (Days)	
If Last Non-Zero Dose Date \leq AE onset date: AE onset date – last non-zero dose date + 1 If Last Non-Zero Dose Date $>$ AE onset date: AE onset date – last non-zero dose date

CONFIDENTIAL

201410

Treatment State	Definition
	If Last Non-Zero Dose Date \leq AE worsening date: AE worsening date – last non-zero dose date + 1 If Last Non-Zero Dose Date $>$ AE worsening date: AE worsening date – last non-zero dose date Missing otherwise.
Duration (Days)	AE Resolution Date – AE Onset Date/AE Worsening Date + 1
Drug-related	If relationship is marked 'YES' on eCRF or if the value is missing.

NOTES:

- AEs that occur or worsen during interruptions of randomized study treatment will be classified as treatment emergent and post-randomization.
- If the last non-zero dose date is missing and the treatment start date is non-missing and the AE onset date or AE worsening date is on or after the treatment start date, then the AE will be considered to be treatment emergent.
- If AE onset date or AE worsening date is missing and AE resolution date is before the treatment start date, then the AE will be classified as Pre-treatment.
- If AE onset date or AE worsening date is missing and AE resolution date is either missing or on or after treatment start date, then the AE will be classified as treatment emergent and post-randomization.

10.4.1.5. Treatment States for Concomitant Medications (Other Than IV Iron Dose Endpoints and Iron Use Summaries)

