BP-related SAEs are those SAEs that have been identified via the BP Exacerbation eCRF page.
General Definitions

 • Post-Randomization last contact date for censoring (subjects not having AE) will be defined as the study completion date.

 • Treatment emergent last contact date for censoring (subjects not having AE) will be defined as follows: 
 ○ 1 day after last non-zero dose date (last non-zero dose date + 1) for subjects not having treatment emergent AE and continuing on study past (last non-zero dose date + 1) ○ Last non-zero dose date for all other subjects

 • AE Patient Years: (Cumulative total of time to AE for subjects who have the AE + Cumulative total of censoring time for subjects without the AE) / 365.25 
 ○ For treatment emergent AEs, the start date of the patient year value for each subject should be the treatment start date. ○ For post-randomization AEs, the start date of the patient year value for each subject should be the randomization date. ○ For follow-up AEs, the start date of the patient year value for each subject should be 2 days after the last non-zero dose date (last non-zero dose date + 2).

 • Incidence Rate (per 100 patient years): $(100 * \text{Number of subjects with at least 1 AE}) / \text{AE person years}$

 • For the analysis of the time to AE onset/worsening, if the AE onset/worsening date is missing then the time to AE onset/worsening will be counted as 1 day.

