10.7.2.1. Handling of Missing and Partial Dates

Element	Reporting Detail
General	Partial dates will be displayed as captured in subject listing displays.
Concomitant Medications	
 • Partial dates for any concomitant medications recorded in the CRF will be imputed using the following convention: 
 ○ If the partial date is a start date, a '01' will be used for the day and 'Jan' will be used for the month ○ If the partial date is a stop date, a '28/29/30/31' will be used for the day (dependent on the month and year) and 'Dec' will be used for the month. • The recorded partial date will be displayed in listings.
Adverse Events	
 • The eCRF allows for the possibility of partial dates (i.e., only month and year or only year) to be recorded for AE start/worsening and end dates. In such a case, the following conventions will be applied for calculating the time to onset and the duration of the event: 
 • Imputing a Start/Worsening Date from a Partial Start/Worsening Date:

CONFIDENTIAL

201410

Element	Reporting Detail

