	
 ○ If an imputed worsening date is before the start date, then the start date will be used as the imputed worsening date. ○ Completely missing stop date: 
 ➤ If only the day is missing, the first of the month will be used unless the Screen Week -2 visit date or treatment start date also occurs in the same month. 
 ● If the treatment start date occurs in the same month, then the treatment start date will be used as the start/worsening date. ● Otherwise, if the Screen Week -2 visit date occurs in the same month, then the Screen Week -2 visit date will be used as the start/worsening date. ➤ If the day and month are missing, then '01' will be used for the day and 'Jan' will be used for the month unless the Screen Week -2 visit date or treatment start date also occurs in the same year. 
 ● If the treatment start date occurs in the same year, then the treatment start date will be used as the start/worsening date. ● Otherwise, if the Screen Week -2 visit date occurs in the same year, then the Screen Week -2 visit date will be used as the start/worsening date. ○ Partial or non-missing stop date is before treatment start date: 
 ➤ If only the day is missing, then the first of the month will be used unless the Screen Week -2 Visit date also occurs in the same month; in this case the Screen Week -2 Visit date will be used as the start/worsening date. ➤ If the day and month are missing, then '01' will be used for the day and 'Jan' will be used for the month unless the Screen Week -2 Visit date also occurs in the same year; in this case the Screen Week -2 Visit date will be used as the start/worsening date. ○ Stop date is partial with the same year (or year and month) as the treatment start date or is on or after the treatment start date: 
 ➤ If only the day is missing, then the first of the month will be used unless the start date of study treatment also occurs in the same month; in this case the study treatment start date will be used as the start/worsening date. ➤ If the day and month are missing, then '01' will be used for the day and 'Jan' will be used for the month unless the start date of study treatment occurs in the same year; in this case the study treatment start date will be used as the start/worsening date. ● Imputing a Stop Date from a Partial Stop Date: 
 ○ Latest of (start date and latest worsening date) is on or before the treatment stop date or is partial with the same year (or year and month) as the treatment stop date:

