
CONFIDENTIAL

201410

Element	Reporting Detail
	
 ➤ If only the day is missing, the last day of the month will be used unless the treatment stop date also occurs in the same month; in this case the treatment stop date will be used as the stop date. ➤ If the day and month are missing, then '31' will be used for the day and 'Dec' will be used for the month, unless the stop date of study treatment also occurs in the same year; in this case the study treatment stop date will be used as the stop date. ○ Latest of (start date and latest worsening date) is partial or non-missing and is after treatment stop date: 
 ➤ If only the day is missing, the last day of the month will be used unless the study conclusion date also occurs in the same month; in this case, the study conclusion date will be used as the stop date. ➤ If the day and month are missing, then '31' will be used for the day and 'Dec' will be used for the month, unless the study conclusion date also occurs in the same year; in this case, the study conclusion date will be used as the stop date. ● Completely missing start or end dates (i.e. no year specified) will remain missing, with no imputation applied. Consequently, time to onset and duration of such events will be missing.
CV Safety Endpoint Events	Discussed in Section 10.6.4

CONFIDENTIAL

201410

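### The AESI time-to-first-onset summary is blanked by a missing resolution date it does not use, and the SAP's rules for partial and missing onset dates disagree

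*SAP*

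**What the plan says.** Four places in the SAP bear on AE onset time.

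- **8.2.3.2 (AESIs Analyses)** lists time to first onset/worsening among the AESI summaries by treatment group and defines it as "The earliest of onset dates for the specific AE – treatment start + 1". It then sets a condition: if the onset or worsening "and/or resolution date is missing or incomplete in the database for any occurrence of the specific AE", then "time to first onset /worsening will be left missing for the subject".
- **10.4.1.4** defines onset time since first dose, for events starting on or after treatment start, as "AE Onset Date - Treatment Start Date + 1". The resolution date enters only the duration variable.
- **10.7.2.1** deals with partial AE dates, and "the following conventions will be applied for calculating the time to onset and the duration of the event". Partial start dates are imputed even where the stop date is wholly missing: "If only the day is missing, the first of the month will be used unless the Screen Week -2 visit date" or the treatment start falls in that month. Wholly missing dates are not imputed: "Consequently, time to onset and duration of such events will be missing".
- **10.6.4.3 (General Definitions)** says that for the analysis of time to onset, "if the AE onset/worsening date is missing then the time to AE onset/worsening will be counted as 1 day".

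No section ranks these rules or ties each to particular outputs.

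**The concern.** A statistic should be missing only when an input to it is missing. Time to first onset has two inputs, onset date and treatment start, and 8.2.3.2 makes it depend on a third date that it never uses.

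The extra condition follows the course of the event. Several AESIs, among them cardiomyopathy, pulmonary artery hypertension, cancer and worsening of hypertension, can remain open at study end. Protocol 7.4.3.3 lets follow-up of serious events and AESIs end at stabilization, another explanation or loss to follow-up as well as at resolution, and those other endings need not yield a resolution date. A summary that keeps resolved events and discards open ones is selected on outcome. If resolution differs between arms, the onset times would not be compared like with like.

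The second problem is reproducibility. Two programmers following different sections would produce different onset times from the same record.

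**Working it through.** The SAP states no figure here to reproduce, so the check applies each rule literally to constructed records. Treatment start is assumed to be 15JAN2019. The formula, from 8.2.3.2 and 10.4.1.4, is onset date − treatment start + 1.

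- **Record A.** One occurrence, onset 10MAR2019, resolution blank. 15JAN to 10MAR is 54 days, so 54 + 1 = 55.
- **Record B.** Onset known only as March 2019, complete resolution date after treatment start. Under 10.7.2.1 the onset becomes 01MAR2019. 15JAN to 01MAR is 45 days, so 45 + 1 = 46.
- **Record C.** Onset date wholly missing.
- **Record D.** First occurrence on 01FEB2019, resolved and fully dated; a later occurrence with resolution blank. 15JAN to 01FEB is 17 days, so 17 + 1 = 18.

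| Record | 8.2.3.2 | Onset formula with 10.7.2.1 | 10.6.4.3 |
|---|---|---|---|
| A | missing | 55 days | not triggered |
| B | missing | 46 days | not triggered (onset partial, not missing) |
| C | missing | missing | 1 day |
| D | missing | 18 days | not triggered |

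**Resolution-date condition.** A and D have complete onset dates and still lose the statistic. D loses it although the first occurrence, which alone sets the answer, is complete. Looking at every occurrence is defensible for onset dates, since an undated occurrence might be the earliest. That argument does not carry over to resolution dates.

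**Conflicts between rules.** 8.2.3.2 and 10.7.2.1 disagree on B. On C, 10.6.4.3 disagrees with both 8.2.3.2 and 10.7.2.1. Each pair of rules therefore conflicts somewhere, but no single record yields three answers.

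**Size.** The documents do not say how many AESI subjects will have an open record. Purely for scale, take 40 AESI subjects (assumed) and let a share f have at least one open record, so that 40 × (1 − f) keep a time to first onset:

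- f = 10%: 40 × 0.9 = 36
- f = 30%: 40 × 0.7 = 28
- f = 50%: 40 × 0.5 = 20

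**The case against.** The strongest reply is that the sections serve different purposes. The 1-day rule sits beside censoring dates, patient-years and incidence rates, where a subject counted as an event needs some time value. 8.2.3.2 governs one line of a descriptive table, and its reference to the database points to dates as recorded, before imputation. 10.7.2.1 is a general event-level convention, and the specific rule would override it. This reading is sensible and may be what was meant, but the SAP does not state it. It also leaves the resolution-date condition unexplained.

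A second reply is that an ongoing event may not have a missing resolution date at all. The AE case report form is not in the documents, and SAP 10.7.2 says that an answer of not applicable is not missing data. This stands in part: equating an ongoing event with a blank resolution date is an inference. It is a reasonable one, because 10.4.1.4 and 10.7.2.1 both provide for absent resolution or stop dates and 8.2.3.2 makes no exception for open events.

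Three stronger readings are tempting, and the documents do not support them:

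- **That subjects with ongoing AESIs drop out of the AESI analysis.** The sentence blanks only time to first onset/worsening. Counts, percentages, rates per 100 person-years, intensity and outcome are not touched by it.
- **That the blanked value carries into person-time or into the cumulative incidence and Kaplan-Meier plots.** Patient-years in 10.6.4.3 do use time to the event, but nothing says the blanked variable is reused. The cumulative incidence plots are optional, and the AESI plots are not made with fewer than 20 subjects in total.
- **That a large share of onset times is lost because several AESIs are chronic.** No share is given, and no difference between arms is shown.

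**Conclusion.** The point holds for one descriptive safety statistic. The resolution-date condition in 8.2.3.2 is a wrong rule as stated, not a missing detail: followed literally, it discards valid onset times according to whether the event resolved. This rests on the assumption that an unresolved AESI leaves the resolution date blank.

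The conflicts over partial and wholly missing onset dates need no such assumption; they follow from the text.

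The number of subjects affected, and any bias between arms, cannot be determined from the documents. The primary and principal secondary analyses are unaffected. The correction should be made because this statistic describes the events the sponsor singled out for scrutiny, and the change is small.

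**What to change.** 1. In 8.2.3.2, delete the words that bring in the resolution date. Reserve that date for duration.
2. In the same sentence, apply the 10.7.2.1 imputation to partial onset and worsening dates, so that an incomplete date no longer blanks the value.
3. For wholly missing onset or worsening dates, reconcile 10.6.4.3 with 10.7.2.1 by naming the outputs each covers. One workable split is Day 1 for rates and time-to-event plots, and missing for descriptive onset-time statistics.

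The cost is SAP wording and the matching derivation specification. No new data are needed, and no other planned analysis changes.

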11. PK sampling will be collected from all subjects randomized to the daprodustat arm at 1 of these 3 visits, Details in Section 7.5.
12. Informed consent for optional genetic research should be obtained before collecting a sample. To minimize potential study bias, the genetic sample should be collected on Day 1.
13. Subjects who are unable to or require assistance to read must not complete the questionnaires.
14. To be completed if available (e.g., translations may be not available in time in all countries).
15. Only SAEs assessed as related to study participation or a GSK product are collected during screening period
16. In circumstances where the new dose of randomized treatment cannot be dispensed on the day of the study visit, the new dose of randomized treatment can be dispensed at next HD treatment. For visits after Day 1, prior randomized treatment should be continued unless on dose hold, Hgb \geq 12 g/dL. Compliance is deferred until randomized treatment is returned
17. For Argentina, ONLY: pregnancy testing will be performed every 4 weeks for FRP as required by local law
18. Biomarker samples will be stored for future analyses for all subjects, except if not permitted by IRB/EC or refused by subject.
19. Informed consent will be obtained prior to any study procedures.

Table 7 TIME AND EVENTS TABLE FOR SUBJECTS THAT PERMANENTLY DISCONTINUE RANDOMIZED TREATMENT

Protocol Activity	Early Treatment Discontinuation Visit (within 2 weeks of the last dose of randomized treatment)	Day 1 – Week 52 (every 12 weeks \pm 2 weeks)	Unscheduled	Follow-up (4 weeks post-study termination \pm 1 week)
Dialysis: In-clinic assessments done pre-dialysis.				
IRT SYSTEM	X			
SBP/DBP ¹ , HR ¹	X (triplicate)	X	X	X
Iron therapy, transfusions ²	X			
Serum pregnancy test (FRP only)	X			
HemoCue Hgb	X	X	X	
Hematology	Hgb only	X		X
Clinical chemistry	X			
Ferritin, serum iron, UIBC, hepcidin, lipids	X			
Hospitalization ² / kidney transplant ²	X	X	X	X
Non-serious AEs, AEs of Special Interest, SAEs, clinical events	X	X	X	X
Review concomitant medications	X	X	X	X
Healthcare resource utilization (subject reporting)	X			
CKD Anemia Symptoms Questionnaire (CKD-AQ) questionnaire, PGI-S, PGI-C ³	X			
SF-36 ³ , EQ-5D-5L ³	X			

1. See Section 7.4.8 for details.

2. Record in eCRF, if applicable

3. Subjects who are unable to or require assistance to read must not complete the questionnaires.

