7.4.3.1. Time period and Frequency for collecting AE and SAE information

- Any SAE assessed as related to study participation (e.g., protocol-mandated procedures, invasive tests, or change in existing therapy) or related to a GSK product will be recorded from the time subject consents to participate in the study up to and including any follow-up contact.
- AEs will be collected from the start of randomized treatment until the Follow-up visit, at the timepoints specified in the Time and Events Table ([Table 6](#)).
- Medical occurrences that begin prior to the start of randomized treatment but after obtaining informed consent will be recorded on the Medical History/Current Medical Conditions section of the eCRF.
- All SAEs will be recorded and reported to PPD within 24 hours, as indicated in [Appendix 8](#).
- Investigators are not obligated to actively seek AEs or SAEs in former study subjects. However, if the investigator learns of any SAE, including a death, at any time after a subject has been discharged from the study, and he/she considers the event reasonably related to the randomized treatment or study participation, the investigator must promptly notify PPD.

NOTE: The method of recording, evaluating and assessing causality of AEs and SAEs plus procedures for completing and transmitting SAE reports to PPD are provided in [Appendix 8](#).

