Pulmonary artery hypertension	Death due to any cause prior to the AESI
Cancer-related mortality and tumor progression and recurrence	All other non-cancer-related death prior to the AESI (use death date as the competing risk date)
Esophageal and gastric erosions	Death due to any cause prior to the AESI
Proliferative retinopathy, macular edema, choroidal neovascularization	Death due to any cause prior to the AESI
Exacerbation of rheumatoid arthritis	Death due to any cause prior to the AESI
Worsening of hypertension	Death due to any cause prior to the AESI

Dot plots displaying the incidence of the event will be provided for AESIs by AESI term and treatment group. The incidence rate in each treatment group and corresponding two-sided 95% confidence interval for the relative risk of the daprodustat group compared to the darbepoetin alfa group will be provided.

Adverse Events

The number and percentage of subjects reporting at least one AE will be provided for each treatment group. These events will be summarized by treatment group, primary system organ class, and preferred term. Pre-treatment and treatment emergent AEs will be summarized separately.

The number and percentage of subjects and the number of occurrences of all treatment emergent AEs will be summarized by primary system organ class, and preferred term.

Summaries of all treatment emergent AEs will be produced for the age group, gender, race group, baseline dialysis type, baseline dialysis start manner, and weight quartile subgroups. Summaries of treatment emergent AEs by subgroup will be produced twice: by system organ class and preferred term and separately by overall frequency.

A listing of AE records for all subjects who reported AEs will be produced.

Summaries of all treatment emergent AEs will be provided by maximum intensity. For AEs reported more than once by a subject, the most severe intensity will be included in summaries where applicable. The max intensity will be presented as “Unknown” if Missing and/or N/A are the only available severity values. Analysis will be repeated for all drug-related treatment emergent AEs.

The number and percentage of subjects reporting the most common treatment emergent AEs (those occurring in $\geq 5\%$ of subjects in any treatment group) will be summarized by preferred term and treatment group.

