10.4.1.4. Treatment States for AE Data

AEs are to be recorded on the eCRF from the start of randomization treatment until the Follow-up visit, at the timepoints specified in the Time and Events table from Section 10.2.1. Serious AEs assessed as related to study participation or related to a GSK product are to be reported on the eCRF from the time a subject consents to participate in the study

CONFIDENTIAL

201410

up to and including any follow-up contact. AE of worsening of an on-going event will be counted once in a particular treatment state.

Treatment State	Definition
Pre-Treatment	
 For subjects with a non-missing screen failure date, if AE onset is on or before the screen failure date: AE Start Date \leq Screen Failure Date For randomized subjects with a missing treatment start date, all AEs are considered pre-treatment For randomized subjects with a non-missing treatment start date, if AE onset date is before treatment start date: AE Start Date $<$ Treatment Start Date
Post-Randomization	
If AE onset date or AE worsening date is on or after the randomization date Randomization date \leq AE Start Date Randomization date \leq AE Worsening Date AE worsening during post-randomization will be defined relative to the maximum intensity of AE prior to randomization date.
 
AE worsening date is the first date in the post-randomization period, when AE intensity increased relative to the maximum intensity of the AE prior to randomization date.

Treatment emergent	
If AE onset date or AE worsening date is on or after treatment start date & on or before the last non-zero dose date plus 1 day. Treatment Start Date \leq AE Start Date \leq Last Non-Zero Dose Date + 1 day Treatment Start Date \leq AE Worsening Date \leq Last Non-Zero Dose Date + 1 day AE worsening during treatment emergent will be defined relative to the maximum intensity of AE prior to randomized treatment start date.
 
AE worsening date is the first date in the treatment emergent period, when AE intensity increased relative to the maximum intensity of the AE prior to randomized treatment start date.

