
Last Non-Zero Dose Date
 
 • Date of last actual dose of randomized study treatment from IP Discontinuation eCRF form. 
 ○ The dose steps used by the dosing algorithm described in the protocol include a dose hold or a zero dose. If subjects are assigned by the algorithm to a zero dose, they do not receive randomized treatment for that period. Hence, it would be possible for a subject to complete the study, while still following the dosing algorithm, but not actually be taking any actual randomized treatment. The last non-zero dose date, then captures the latest date in the study that a subject physically took a dose of randomized treatment. • The eCRF allows for the possibility of partial or missing dates to be recorded for the last actual dose of randomized study treatment on the IP Discontinuation form (i.e., missing day, or day and month, or day and month and year). In such a case, or in case of subjects who have a non-missing treatment start date, but are missing an IP Discontinuation form, the following conventions will be applied in order to impute a last non-zero dose date: 
 ○ Missing day: 
 ▪ The last day of the month will be used, unless the treatment stop date also occurs in the same month; in this case, the treatment stop date will be used. ○ Missing day and month; 
 ▪ ‘31’ will be used for the day and ‘Dec’ will be used for the month, unless the treatment stop date also occurs in the same year; in this case the treatment stop date will be used. ○ Missing day, month, and year: 
 ▪ Treatment stop date will be used only for subjects who have a non-missing treatment start date.

CONFIDENTIAL

201410

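### The by-arm cancer AESI count and rate stop one day after the last dose taken, which omits cancers found after stopping and can drop cancers found between darbepoetin injections

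*SAP*

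**What the plan says.** - **Display.** SAP 8.2.3.2 gives each AESI by treatment group as a number, a percentage and a rate per 100 person-years, and then limits it: "These summaries of special interest AEs will be provided for those AEs classified as treatment emergent". For AEs in general it says: "Pre-treatment and treatment emergent AEs will be summarized separately". It assigns no table to any later AE state.
- **Window.** Under SAP 10.4.1.4, onset or worsening must fall "on or before the last non-zero dose date plus 1 day". SAP 10.6.1 says this date "captures the latest date in the study that a subject physically took a dose of randomized treatment". For an injection, that is the day it was given, not the end of its dosing interval. SAP 10.6.4.3 censors event-free person-time at the same point.
- **Collection.** Protocol 7.4.3.1: "AEs will be collected from the start of randomized treatment until the Follow-up visit". Table 7 of Protocol 7.1, for subjects who have stopped permanently, marks "Non-serious AEs, AEs of Special Interest, SAEs, clinical events" at every visit type, including Follow-up.
- **Unused states.** SAP 10.4.1.4 also defines Post-Randomization and Follow-up states, and 10.6.4.3 gives their patient-years and a censoring rule: "Post-Randomization last contact date for censoring (subjects not having AE) will be defined as the study completion date".
- **Dot plots.** SAP 8.2.3.2: "Dot plots displaying the incidence of the event will be provided for AESIs by AESI term and treatment group". These carry a relative risk but name no AE state.
- **Forced stop.** Protocol 5.5 makes a new or recurrent cancer a reason for permanent discontinuation, except localized squamous or basal cell skin cancer. Daprodustat is taken daily (Protocol 6.1). Darbepoetin is injected every 4 weeks, every 2 weeks or weekly, depending on dose step (Protocol 12.3.1).

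**The concern.** Protocol Appendix 4 lists cancer as a potential risk of daprodustat and notes raised cancer morbidity and mortality with rhEPO in patients who have cancer. The by-arm AESI table is where a reader would look for a comparison. A one-day tail suits a disease poorly when it may be diagnosed well after it began. The same SAP allows 28 days after the last dose for on-treatment cardiovascular endpoints (10.4.1.2).

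Two things are at stake. First, cancers found after stopping are collected but do not reach the table in either arm. Second, the diagnosis itself ends dosing, so the event closes its own window. On daily tablets the last dose is normally the same day or the day before. On darbepoetin it is the previous injection, which may be weeks earlier.

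**Working it through.** The plan states no figure for this window, so there is none to reproduce. The steps below apply its definitions.

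**1. Follow-up outside the window.** Inputs: 300 randomized and up to about 30% stopping before Week 28 (Protocol 9.2.1); 52 weeks of treatment; Follow-up from Week 56 (Table 6). Assumptions: mean stop at Week *s*; every stopper followed to Week 56; no stopping after Week 28; both arms treated as dosed daily; 52.18 weeks per year.

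Share outside to Week 56 = [0.30 × (56 − s) + 0.70 × 4] / 56

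- s = 14: (12.6 + 2.8)/56 = 27.5%
- s = 28: (8.4 + 2.8)/56 = 20.0%
- s = 5: (15.3 + 2.8)/56 = 32.3%

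In patient-years over both arms at s = 14:

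- outside: (90 × 42 + 210 × 4)/52.18 = 88.5
- inside: (210 × 52 + 90 × 14)/52.18 = 233.4

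The documents give no cancer rate. At an assumed 1 to 4 per 100 patient-years, 0.9 to 3.5 cases fall outside and 2.3 to 9.3 inside. This measures events left out. It does not measure bias in the rate, because the denominator is cut at the same point.

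**2. Scheduled end of treatment.** Table 6 marks no dispensing at Week 52. By schedule, a completer's last injection is at Week 48, 50 or 51, while tablets run to about Week 52. With equal true rates and evenly spread onset, the daprodustat:darbepoetin count ratio among completers is 52/48 = 1.08, 52/50 = 1.04 or 52/51 = 1.02. The rate is unaffected by this alone. Even at 4 per 100 patient-years with all darbepoetin 4-weekly, the loss is (233.4/2) × 0.04 × (4/52) = 0.36 case; at 1 per 100 it is 0.09.

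**3. Cancer that stops dosing between injections (illustration only).** Assume onset is dated at diagnosis and diagnoses fall evenly over an interval of *d* days. Only the injection day and the next day lie inside, so the share inside is 2/d: 7% (28 days), 14% (14 days) or 29% (7 days). On daily tablets it is about 100%. Let *g* be the share of on-treatment cancers that end dosing before the next injection. The apparent daprodustat:darbepoetin ratio with equal true risk is 1/[(1 − g) + g × 2/d]:

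| Interval | g = 10% | g = 25% | g = 50% |
|---|---|---|---|
| 4-weekly | 1.10 | 1.30 | 1.87 |
| 2-weekly | 1.09 | 1.27 | 1.75 |
| weekly | 1.08 | 1.22 | 1.56 |

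Unlike step 2, this also affects the rate: the event leaves the numerator while almost all of the subject's person-time stays.

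**4. Other outputs.**

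- The SAE, fatal SAE and AE-leading-to-discontinuation tables in SAP 8.2.3.2 are also treatment emergent only.
- The cumulative incidence plots are optional and are dropped below 20 subjects, so at the counts in step 1 they would not appear.
- Discontinuation reasons by arm (SAP 6.2.2), adjudicated cause of death (8.2.2.4), the AE listing and IDMC reports of SAEs (Protocol 9.4.5) each show part of the picture. None is a by-arm cancer count and rate over all follow-up.

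**The case against.** A treatment-emergent summary is a coherent on-drug choice. It applies to every AESI, and its numerator and denominator stop together. That stands, and it is why the table should stay.

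The cancers are also not lost to view. Protocol 12.8.2 names malignant cancers as an example of an SAE, and the IDMC receives unblinded SAE reports, with no treatment-emergent limit stated. Discontinuation reasons are tabulated by arm in the ITT population and should reveal forced stops. AEs during temporary interruptions do count as treatment emergent (SAP 10.4.1.4). All of this stands as partial coverage.

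The ratios in step 3 depend wholly on the assumed onset dating and the assumed *g*. The cancer AESI term list (SAP 10.6.4.3) also includes terms such as cytopenia and pancytopenia, which Protocol 5.5 does not make a reason to stop. The exempt skin cancers force no stop either. This objection succeeds against any claimed size, but not against the direction.

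The 27.5% is not a bound. Deaths and withdrawals would lower it; stopping after Week 28 or long darbepoetin intervals would raise it.

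A reader might infer that the Post-Randomization censoring rule ends at Week 52, because SAP 10.7.1 defines completion through that visit. The documents do not establish this. SAP 10.6.1 takes the date from the Study Conclusion form, or from last contact if it is entirely missing. The rule also covers only subjects without the event, so an early date would trim person-time and would not drop cancers.

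**Conclusion.** The concern holds as a gap in one safety display. Cancers first found after stopping are collected but left out of the by-arm cancer count and rate in both arms. A cancer dated between darbepoetin injections can drop out of that arm's numerator when the same event on daprodustat would normally stay in. The second effect tends to raise daprodustat's apparent relative cancer count and rate.

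The omitted cases number about 1 to 4 over both arms, given 30% stopping at a mean of Week 14, full follow-up and an assumed 1 to 4 cancers per 100 patient-years. The between-arm effect cannot be sized: onset dating, the darbepoetin dose mix and the share of AESI terms that force a stop are not in the documents. The scheduled end gap is minor and affects counts only.

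Two stronger readings are tempting. One is that the plan shields daprodustat from a cancer signal. The documents do not support it: the asymmetry works against daprodustat, and the early cut-off applies to both arms. The other is that a ratio near 1.9 should be expected. That figure needs half of on-treatment cancers to stop dosing before the next injection, with every injection 4-weekly and onset dated at diagnosis, and the documents establish none of these. This is a cheap improvement to safety reporting and does not touch the primary objective.

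**What to change.** Keep the treatment-emergent table and add to SAP 8.2.3.2:

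> The cancer AESI will also be summarised by treatment group in the Post-Randomization state, Safety population (number, percentage, rate per 100 patient-years, relative risk). Events and person-time both run to the Follow-up visit, or to withdrawal or death if earlier, and that date is the censoring date for this display.

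Setting one end date for this display keeps numerator and denominator matched, whatever the study completion date turns out to mean. For a completer, both arms then share one window of 56 to 58 weeks. A few words stating which AE state the dot plots use would also help.

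The cost is SAP wording and one descriptive display, from data already collected and an AE state already defined. The downside is that off-treatment events dilute an on-drug rate. With few events expected, the new display should be read as supplementary to the existing table.
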